16.2.3. MAIN ANALYSIS OF SECONDARY EFFICACY ENDPOINTS

Refer to Section 7.4 for more information about the hierarchical testing procedure that will be used to test the three key secondary hypotheses. Only nominal p-values will be provided for the non-key secondary endpoints.

16.2.3.1. Binary Endpoints

For the incidence of patients with oxygen-free recovery at Day 29 (refer to Section 16.2.1.1), incidence of patients with ≥ 2 -point improvement from baseline or fit for discharge on the ordinal scale at Day 29 (refer to Section 16.2.1.2), incidence of all-cause mortality through Day 29 (refer to Section 16.2.1.3), incidence of patients with clinical recovery at Days 8, 15 and 29 (refer to Section 16.2.1.8), and incidence of patients with sustained clinical recovery as confirmed by Day 60 follow-up (refer to Section 16.2.1.9), the number and percentage of patients with and without the event will be provided by treatment arm. For the incidence of all-cause mortality, primary reason of death will also be summarized by treatment arm.

For each of these endpoints, a logistic regression will be performed to test the difference between a candidate agent plus SoC and placebo plus SoC treatment arms, including the baseline clinical severity of 2 on the 8-point ordinal

scale for clinical severity (yes or no) stratification variable, remdesivir use at baseline (yes or no) stratification variable, both as captured on the IWRS, country (region; refer to Section 7.5), and treatment arm as factors. The estimate of the relative risk (risk difference) between the two treatment arms, the corresponding two-sided 95% Wald CI, and the p-value obtained from the logistic regression model will be provided.

The odds ratio (of candidate agent plus SoC vs. placebo plus SoC) for having the event at the specified Day and its two-sided 95% CI will also be presented.

16.2.3.2. Ordinal Endpoints

For the incidence of patients in each category of the 8-point ordinal scale for clinical severity at Days 8, 15, and 29 endpoints (refer to Section 16.2.1.4), the number and percentage of patients in each ordinal scale category will be provided at each specified Day for each treatment arm and will be analyzed using a proportional odds model, including the baseline clinical severity of 2 on the 8-point ordinal scale for clinical severity (yes or no) stratification variable, remdesivir use at baseline (yes or no) stratification variable, both as captured on the IWRS, country (region; refer to Section 7.5), and treatment arm as factors.

The odds ratio (candidate agent plus SoC vs. placebo plus SoC) of having a higher score than any given category *k* of the ordinal scale at Days 8, 15, and 29, their two-sided 95% CI, and associated p-value will be presented for each specified Day, where it is assumed that the odds ratio does not differ depending upon *k*.

[figure not shown]
The worst post-baseline score on the 8-point ordinal scale for clinical severity from randomization to Day 29 (refer to Section 16.2.1.5) and each “number of days” endpoint (refer to Sections 16.2.1.6 and 16.2.1.7) will be summarized and analyzed similarly.

Shift tables from baseline to each post-baseline day up to Day 29 as well as to the worst post-baseline score will also be provided for the 8-point ordinal scale for clinical severity.

16.2.4. SENSITIVITY ANALYSES FOR SECONDARY EFFICACY ENDPOINTS

The following sensitivity analyses to the main analysis of each key secondary efficacy endpoint will be performed. No sensitivity analyses will be performed for the non-key secondary efficacy endpoints.

- **Sensitivity to stratification variables:** The main analysis of each key secondary efficacy endpoint will be repeated but the stratification variables as derived based on the eCRF data (refer to Section 7.6) will be included in the model instead of the stratification variables as captured on the IWRS if at least 10% of patients are mis-

stratified at the time of randomization for a stratification variable.

• **Sensitivity analysis to missing data assumption #1:**

- For the incidence of patients with oxygen-free recovery at Day 29 (refer to Section 16.2.1.1), a multiple imputation approach will be applied to impute the missing oxygen-free recovery status (yes or no) at Day 29 for subjects who discontinued from study before or on Day 29 using a logistic regression including effects for the treatment arm, baseline clinical severity of 2 on the 8-point ordinal scale for clinical severity stratification variable (yes or no), remdesivir use at baseline stratification variable (yes or no), both as captured on the IWRS, and country (or region; refer to Section 7.5). One hundred (100) imputed datasets will be generated using a seed of 2504.

Each imputed dataset will then be analyzed using the same model as for the main analysis of this key secondary efficacy endpoint (refer to Section 16.2.3.1).

The relative risks and parameter estimates for the effects of the logistic regression model and their SEs will then be combined using the Rubin’s rule to obtain a combined estimate of the treatment arm effect and its SE, and the associated p-value will be provided. The relative risks and odds ratios will first be log transformed and then combined to obtain a combined relative risk and combined odds ratio, and their associated 95% CI. The combined relative risk and combined odds ratio, and associated 95% CI, will be back-transformed before being displayed;

- For the incidence of patients with ≥ 2 -point improvement from baseline or fit for discharge on the ordinal scale at Day 29 (refer to Section 16.2.1.2), the same sensitivity analysis using multiple imputation as described above as for the key secondary efficacy endpoint of incidence of patients with oxygen-free recovery at Day 29 will be performed for this key secondary efficacy endpoint, but using a seed of 1228 ;
- For the incidence of all-cause mortality through Day 29 (refer to Section 16.2.1.3), the same sensitivity analysis using multiple imputation as described above as for the key secondary efficacy endpoint of incidence of patients with oxygen-free recovery at Day 29 will be performed for this key secondary efficacy endpoint, but using a seed of 2007.

• **Sensitivity analysis to missing data assumption #2:**

- For the incidence of all-cause mortality through Day 29, a tipping point analysis will be performed. For patients who discontinued early from the study, all possible combinations of the number of patients

CCI

PPD

Version Number: Amendment 1, v1.0
Version Date: 23Apr2021

CCI

dead or alive at Day 29 will be considered and the main analysis of this key secondary efficacy endpoint will be repeated for each combination.

A dot plot will be produced with number of patients with unknown death status at Day 29 imputed to death for the shared placebo plus SoC treatment arm reported on the x-axis and number of patients with unknown death status at Day 29 imputed to death for the candidate agent plus SoC treatment arm reported on the y-axis, and distinguishing between combination that results in statistically significant treatment effect (a dot is displayed for the combination) vs. not statistically significant treatment effect (no dot is displayed for the combination). The clinical plausibility of the combinations on the boundary will be discussed in the clinical study report (CSR) to evaluate robustness of study conclusions to missing data.

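### The multiple imputation for the key secondary endpoints repeats the analysis model's terms, so it gives essentially the complete-case odds ratio and leaves collected post-baseline status unused

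*SAP*

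**What the plan says.** For the first key secondary endpoint, Master SAP 16.2.4 states that "a multiple imputation approach will be applied to impute the missing oxygen-free recovery status". Only patients who leave the study by Day 29 are imputed. The model is specified as "using a logistic regression including effects for the treatment arm, baseline clinical severity of 2 on the 8-point ordinal scale". Remdesivir use at baseline and country or region are its other two terms. The plan uses 100 imputed datasets and Rubin's rules, and "Each imputed dataset will then be analyzed using the same model as for the main analysis of this key secondary efficacy endpoint". The 2-point or fit-for-discharge endpoint and mortality receive "the same sensitivity analysis using multiple imputation as described above", each with its own seed.

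Master SAP 16.2.3.1 gives the main model: "a logistic regression will be performed to test the difference between a candidate agent" and placebo, with the two stratification variables, "both as captured on the IWRS, country (region; refer to Section 7.5), and treatment arm as factors".

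The main missing-data rules are in 16.2.2.1:
- **Oxygen-free recovery:** unknown status counts as not met.
- **2-point or fit-for-discharge:** a last score of 7 (not hospice) or 8 counts as met. Any other missing Day 29 score counts as not met.
- **Mortality:** unknown counts as alive, except after discharge to hospice.

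For mortality, 16.2.4 adds a tipping-point analysis over every dead/alive combination of the discontinuers. The other two endpoints have no further missing-data analysis. The ordinal scale is scored daily in hospital and again at Days 15 and 29 (Protocol 1.3).

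**The concern.** An imputation adds information about the treatment effect only if its model knows something that the analysis model does not. Here the two models share the same four terms, and none is measured after baseline. Take two patients in the same arm, with the same strata and country. One leaves while on high-flow oxygen; the other is lost after going home with a score of 8. Both are imputed with the same chance of oxygen-free recovery.

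The SAP itself treats later status as informative, because 16.2.2.1 uses the last score or hospice discharge for two of the three endpoints. At stake is how far this analysis can support the main result. Oxygen-free recovery is the first key secondary test and gates the other two (Master SAP 7.4). This imputation is the only planned missing-data sensitivity analysis for it and for the 2-point endpoint.

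**Working it through.** **Step 1. The plan's own figure.** Master SAP 7.1 assumes 65% versus 74.7% (65 + 9.7) with 350 per arm; 7.3 sets two-sided 0.05. The mean rate is 0.6985. The standard error under the null is √(2 × 0.6985 × 0.3015 / 350) = 0.03469, and under the alternative √((0.65 × 0.35 + 0.747 × 0.253) / 350) = 0.03450. Then z = (0.097 − 1.96 × 0.03469) / 0.03450 = 0.84, which gives power 0.7998, as stated. The other two key secondary figures give 0.7997 and 0.797.

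**Step 2. The two models side by side.**

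| Term | Imputation (16.2.4) | Analysis (16.2.3.1) |
|---|---|---|
| Treatment arm | yes | yes |
| Baseline severity of 2 | yes | yes |
| Remdesivir at baseline | yes | yes |
| Country or region | yes | yes |
| Any post-baseline status | no | no |

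**Step 3. Why the result is complete-case.** The complete-case estimate b solves Σ x(y − p(b)) = 0 over observed patients. Imputed outcomes are drawn with mean close to p(b) from the same x, so their contribution Σ x(y* − p(b)) averages about zero. The completed data are therefore solved by b again, plus Monte Carlo noise. This does not depend on the dropout rate.

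**Step 4. Simulation.** There were 350 per arm, 100 trials per row and 100 imputations. The following are assumptions, not figures from the documents:
- 12% have severity 2, half are on remdesivir, and there are three regions.
- Recovery is about 66% on control and 74% on active.
- An earlier clinical status is known for everyone. Day 29 recovery is 90% if it is favourable and 20% if not.

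Relative dropout weights, scaled to the overall rate:
- **A:** both arms, unfavourable 2.0, favourable 0.5.
- **B:** both arms, favourable 1.4, unfavourable 0.4.
- **C:** arms differ. Active: unfavourable 2.2, favourable 0.5. Control: favourable 1.4, unfavourable 0.5.

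Mean log odds ratios:

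| Pattern, missing | Full data | Complete case | MI as planned | MI plus earlier status | Missing = not met |
|---|---|---|---|---|---|
| A, 10% | 0.396 | 0.393 | 0.393 | 0.404 | 0.364 |
| B, 10% | 0.397 | 0.402 | 0.402 | 0.397 | 0.295 |
| C, 5% | 0.407 | 0.498 | 0.498 | 0.409 | 0.479 |
| C, 10% | 0.414 | 0.610 | 0.610 | 0.416 | 0.565 |
| C, 15% | 0.418 | 0.729 | 0.730 | 0.425 | 0.634 |

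Over all three patterns at 5, 10 and 15% missing, the planned MI and complete case differed by 0.003 to 0.006 on average and by at most 0.021 in any trial. Their standard errors agreed to about 0.001. In row C at 10%, the risk difference was 8.3 points with full data, 12.1 with the planned MI and 8.3 with earlier status added; the standard error fell from 0.182 to 0.176.

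**Step 5. The sequential version.** In a separate simulation with no treatment effect (15 imputations), the planned MI gave a mean log odds ratio of 0.133. Imputing through Day 8 and Day 15 status gave 0.007, with no loss of precision.

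**The case against.** The strongest reply is that this analysis is meant to be read against the main rule, and that missing at random versus missing = not met is a legitimate contrast. That stands. Take a null effect with dropout among not-yet-discharged patients of 20% on active and 6% on control, and 3% among discharged patients. The planned MI gives an odds ratio of 1.12 to 1.13 and the main rule 0.92 to 0.93. With more dropout on control, the main rule gives 1.08 to 1.09 and complete case 0.89 to 0.91. The two bracket the truth, so their disagreement would show. A reader might infer that the plan cannot detect informative dropout at all; the documents do not support that. The contrast is not guaranteed either: in pattern C both estimates exceed the full-data value (0.610 and 0.565 against 0.414).

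A reader might also infer an inflated false-positive rate for the key secondary tests. In the null scenario with more active-arm dropout, the planned MI rejected one-sided in 7.8% of trials (nominal 2.5%). But formal testing uses the main analysis, which rejected in 0.5 to 0.9%. The 7.8% belongs to an analysis that carries no claim.

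Other limits also stand:
- The trial is double-blind and patients who stop treatment stay in the study (Protocol 7.1), so a large arm difference in dropout is not to be presumed. When dropout follows status equally in both arms, the log odds ratio barely moves (pattern A, 0.393 against 0.396).
- Baseline severity of 2 is in the model, so only post-baseline status, or severity within Grades 3 to 5, is missed.
- Mortality has its tipping-point analysis.
- The primary-endpoint imputation in 16.1.4 is delta-adjusted, so this point does not extend to it.

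**Conclusion.** The point holds in a limited form. The match between the planned imputation and complete case follows from the text and needs no assumption about dropout. It is near-exact for the odds ratio; standardised risks differ slightly (for example 0.704 against 0.701). It concerns discontinuers only, because 16.2.4 does not impute status missing for other reasons.

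The bias is conditional. It is material mainly when status-driven dropout differs by arm. In pattern C it is 0.091, 0.196 and 0.312 on the log odds ratio at 5, 10 and 15% missing (0.498 − 0.407, 0.610 − 0.414, 0.730 − 0.418). Because the documents state neither a dropout rate nor a mechanism, these sizes are illustrative.

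The gap matters most for oxygen-free recovery and the 2-point or fit-for-discharge endpoint. In practice it bears on COV-01-004, whose SAP takes its efficacy analyses from the Master SAP; the COV-01-001 and COV-01-005 SAPs run no sensitivity analyses (16.2.4 in each). The analysis is not useless, but a better one is available from data already collected, and the change should be made.

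**What to change.** In Master SAP 16.2.4, replace the single-step imputation with sequential multiple imputation (monotone or fully conditional). Keep the four existing terms and add the ordinal score at fixed days before Day 29, for example Day 8 and Day 15. Group the scores so that 6 has a place, flag discharge to hospice, and collapse sparse categories. Impute any missing earlier score first, then Day 29 status, and analyse with the unchanged main model. A patient discharged before Day 8 has no scheduled score that day, so state how it is set; 16.2.2.2 already has a carry-forward rule that could serve while the patient remains in the study.

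Do not use day of discontinuation or last non-missing score as covariates. Completers have no discontinuation day, and their last score by Day 29 is the Day 29 score that helps define the outcome, so the imputation model could not be fitted sensibly.

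The cost is modest extra programming on data already collected. The main analysis and the alpha are untouched.

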16.2.5. SUPPLEMENTARY ANALYSES FOR SECONDARY EFFICACY ENDPOINTS

The main analysis of each key secondary efficacy endpoint will be repeated for each subgroup defined in Section 7.7. For subgroups corresponding to one of the factors included in the main model, the corresponding factor will be excluded from the model. For example, the remdesivir use at baseline (yes/no) stratification variable, as captured on the IWRS, will not be included in the analysis of the patients who received remdesivir at randomization subgroup, as captured on the IWRS, and analysis of the patients who did not receive remdesivir at randomization subgroup, as captured on the IWRS.

The following supplementary analyses will also be performed for the incidence to all-cause mortality key secondary efficacy endpoint:

- For the incidence of all-cause mortality through Day 29, the time to all-cause death, in days, will be derived as follows:

- Time to all-cause mortality (days) =

$$(\text{Date of all-cause death/Date of censoring} - \text{Date of Study Day 1 [refer to Section 6.1]}) + 1.$$

The date of death will be taken from data captured on the *Death Details* page of the eCRF.

[figure not shown]
For patients who were alive on Day 29, time to all cause-mortality will be censored at Day 29. For patients with an unknown alive status at the time of the analysis due to missing data, time to all-cause mortality will be censored at the latest date on which the patient was known to be alive before or on the data cut-off date of the analysis. The last date the patient was known to be alive will be the latest date

CCI

PPD

Version Number: Amendment 1, v1.0
Version Date: 23Apr2021

CCI

collected on any page of the eCRF. For patients who discontinued from the study before the time of the analysis, time to all-cause mortality will be censored at the date of study discontinuation, as captured on the *Disposition* page of the eCRF.

Number and percentage of patients with and without the event will be presented by randomized treatment arm. For patients who did not meet the event, the main reason for censoring will be summarized similarly.

The incidence of all-cause mortality through Day 29 along with its two-sided 95% CI by treatment arm will then be estimated using Kaplan-Meier survival curves of the time to all-cause mortality. Kaplan-Meier survival curves by treatment arm will also be provided.

The 25th percentile, 50th percentile (median), and 75th percentile of time to all-cause mortality (days) with the corresponding two-sided 95% CIs based on the Kaplan-Meier survival curves (refer to Section 16.2.4) for each treatment arm will also be presented. The estimate of the SEs will be computed using Greenwood's formula, the CI for the median will be calculated according to Brookmeyer and Crowley (1982) and the other CIs will be derived from the Kaplan-Meier estimates using the log-log transformation.

[figure not shown]
A Cox proportional hazard model will be performed, including the baseline clinical severity of 2 on the 8-point ordinal scale for clinical severity (yes or no), remdesivir use at baseline (yes or no) stratification variables, both as captured on the IWRS, country (region), and treatment arm as factors. Ties will be handled using the exact method. The hazard ratio of the candidate agent plus SoC vs. placebo plus SoC, its associated two-sided 95% CI, and p-value will be provided.

No supplementary analyses will be performed for the non-key secondary efficacy endpoints.

16.3. EXPLORATORY EFFICACY

16.3.1. EXPLORATORY EFFICACY ENDPOINTS

CCI

CCI

PPD

Version Number: Amendment 1, v1.0
Version Date: 23Apr2021

CCI

CCI [Redacted]

Master Statistical Analysis Plan

CCI [Redacted]

CCI [Redacted]

PPD [Redacted]

Version Number: Amendment 1, v1.0
Version Date: 23Apr2021

CCI [Redacted]

[Redacted]

[figure not shown]
[Redacted]

CCI

Master Statistical Analysis Plan

CCI

CCI

PPD

CCI

Version Number: Amendment 1, v1.0
Version Date: 23Apr2021

CCI [Redacted]

Master Statistical Analysis Plan

CCI [Redacted]

CCI [Redacted]

PPD [Redacted]

Version Number: Amendment 1, v1.0
Version Date: 23Apr2021

CCI [Redacted]

[Redacted]

[Redacted]

[Redacted]

CCI [Redacted]

Master Statistical Analysis Plan

CCI [Redacted]

CCI [Redacted]

PPD [Redacted]

Version Number: Amendment 1, v1.0
Version Date: 23Apr2021

CCI [Redacted]

[Redacted]

[Redacted]

[Redacted]

CCI [Redacted]

Master Statistical Analysis Plan

CCI [Redacted]

CCI [Redacted]

PPD [Redacted]

Version Number: Amendment 1, v1.0
Version Date: 23Apr2021

CCI [Redacted]

[Redacted]

[Redacted]

CCI [Redacted]

Master Statistical Analysis Plan

CCI [Redacted]

CCI [Redacted]

PPD [Redacted]

Version Number: Amendment 1, v1.0
Version Date: 23Apr2021

CCI [Redacted]

[Redacted]

[Redacted]

CCI [Redacted]

Master Statistical Analysis Plan

CCI [Redacted]

CCI [Redacted]

PPD [Redacted]

Version Number: Amendment 1, v1.0
Version Date: 23Apr2021

CCI [Redacted]

[Redacted]

[figure not shown]
[Redacted]

CCI

Master Statistical Analysis Plan

CCI

CCI

PPD

[figure not shown]

Version Number: Amendment 1, v1.0
Version Date: 23Apr2021

CCI

[figure not shown]

CCI

Master Statistical Analysis Plan

CCI

CCI

PPD

Version Number: Amendment 1, v1.0
Version Date: 23Apr2021

CCI

CCI [Redacted]

16.3.4. SENSITIVITY ANALYSES FOR EXPLORATORY EFFICACY ENDPOINTS

CCI [Redacted]

16.3.5. SUPPLEMENTARY ANALYSES FOR EXPLORATORY EFFICACY ENDPOINTS

CCI [Redacted]

16.4. ADDITIONAL EFFICACY

16.4.1. ADDITIONAL EFFICACY ENDPOINT

16.4.1.1. Incidence of All-Cause Mortality through Day 60

An additional efficacy endpoint is the incidence of all-cause mortality through Day 60, defined as the proportion of patients having died due to any cause before or on Day 60. Patients death before or at Day 60 will be based on data captured on the *Death Details* page of the eCRF.

16.4.2. MISSING DATA IMPUTATION METHOD FOR ADDITIONAL EFFICACY ENDPOINT

Patients with an unknown alive/death status at Day 60 will be considered as alive at Day 60.

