scale score, while patients with a score of 7 discharged to hospice care will be considered as not having met the event, also regardless of their change from baseline in ordinal scale score. For patients hospitalized and not considered as fit for discharge at Day 29 i.e., patients with an ordinal scale score < 6, the ‘≥ 2-point improvement from baseline’ requirement (yes or no) will be established based on the patient’s change from baseline in the ordinal scale at Day 29, where change from baseline will be computed as defined in Section 6.5.

Refer to Section 16.2.2.1 for handling of missing ≥ 2-point improvement from baseline or fit for discharge on the 8-point ordinal scale for clinical severity status.

16.2.1.3. Incidence of All-Cause Mortality through Day 29

The third key secondary efficacy endpoint is the incidence of all-cause mortality through Day 29, defined as the proportion of patients having died due to any cause before or on Day 29. Patients’ alive/death status by Day 29 will be determined based on data captured on the *Death Details* page of the eCRF. If a patient does not have any data captured on the *Death Details* page of the eCRF by Day 29 but his/her ‘subject status’ captured on the *Contact* page of the eCRF at Day 29 is alive or he/she had some data captured on any other page of the eCRF on or after Day 29, he/she will be considered alive on Day 29.

Refer to Section 16.2.2.1 for handling of missing alive/death through Day 29 status.

[figure not shown]
16.2.1.4. Distribution of Patients across the Categories of the 8-point Ordinal Scale for Clinical Severity at Days 8, 15, and 29

An ‘other secondary efficacy endpoint’ is the distribution of patients across the categories of the 8-point ordinal scale for clinical severity at Days 8, 15, and 29 i.e., the proportion of patients in each category of the 8-point ordinal scale for clinical severity at Days 8, 15, and 29. It is to be noted that patients with a score of 7 discharged to hospice care will be pooled with patients with a score of 1 (death) for this ‘other secondary efficacy endpoint’.

Refer to Section 16.1.1 for the description of the 8-point ordinal scale and to Section 16.2.2.1 for handling of missing ordinal scale scores.

16.2.1.5. Worst Post-Baseline Score on 8-point Ordinal Scale from Baseline to Day 29

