16.2.2. MISSING DATA IMPUTATION METHOD FOR SECONDARY EFFICACY ENDPOINTS

16.2.2.1. Binary Endpoints

For the *incidence of oxygen-free recovery at Day 29* endpoint, the algorithm defined in Section 16.2.1.1 will first be applied. Then, patients with a missing oxygen-free recovery status at Day 29 will be considered as not having met the event for this key secondary efficacy endpoint.

For the *incidence of patients with ≥ 2-point improvement from baseline or fit for discharge on the ordinal scale at Day 29* endpoint (refer to Section 16.2.1.2), patients with a missing ordinal scale score at Day 29 due to patient’s death, discontinuation from study before or on Day 29 or for any other reason (with the following exception) will be considered as not having met the event at Day 29 for that key secondary endpoint. The only exception is for patients with a missing ordinal scale score at Day 29 for which the latest non-missing ordinal scale score before Day 29 was 7 (but not discharge to hospice care) or 8. These patients will be assumed to be fit for discharge at Day 29 and so, as having met the event.

For the *incidence of all-cause mortality through Day 29* endpoint (refer to Section 16.2.1.3), patients with an unknown alive/death status at Day 29 due to discontinuation from study for a reason other than death or missing data will be considered as alive in the analysis, exception of patients for who the last-missing ordinal scale score was 7 and that have been discharged to hospice care before discontinuing from study before Day 29. These patients will be considered as dead at Day 29 for the main analysis of this key secondary efficacy endpoint.

[figure not shown]
For the *clinical recovery by Day 8* endpoint (refer to Section 16.2.1.8), any patient who died before or on Day 8, discontinued from study before or on Day 8 or with missing clinical recovery status at Day 8 will be considered as not having clinical recovery by Day 8. Missing *clinical recovery by Days 15 and 29* will be handled similarly.

For the *sustained clinical recovery as confirmed by Day 60* follow-up endpoint (refer to Section 16.2.1.9), any patient who died before or on Day 60, discontinued study before Day 60 or with a missing 8-point ordinal scale score at Day 60 will be counted as not having sustained clinical recovery.

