16.4.2. MISSING DATA IMPUTATION METHOD FOR ADDITIONAL EFFICACY ENDPOINT

[figure not shown]
Details are provided in the Master COV-01 SAP.

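### The missing-data rules for all-cause mortality can count one patient as dead through Day 29 and alive through Day 60

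*SAP*

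**What the plan says.** **Day 29.** Master SAP Section 16.2.1.3 makes mortality the third key secondary endpoint, "defined as the proportion of patients having died due to any cause before or on Day 29". Under Section 16.2.2.1, "patients with an unknown alive/death status at Day 29 due to discontinuation from study for a reason other than death or missing data" are taken as alive. There is one carve-out: "exception of patients for who the last-missing ordinal scale score was 7 and that have been discharged to hospice care before discontinuing from study" (the discontinuation has to precede Day 29). For that group the SAP says: "These patients will be considered as dead at Day 29 for the main analysis of this key secondary efficacy endpoint". (The phrase about the last-missing score appears to mean the last non-missing score.)

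**Day 60.** Section 16.4.1.1 defines the additional endpoint in parallel terms, "defined as the proportion of patients having died due to any cause before or on Day 60". The source is the Death Details page: "Patients death before or at Day 60 will be based on data" captured there. Section 16.4.2 then gives the whole missing-data rule: "Patients with an unknown alive/death status at Day 60 will be considered as alive at Day 60". Section 16.4.3 plans percentages with confidence intervals, a relative risk and an odds ratio, without inference. Section 16.4.4 plans no sensitivity analysis.

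**COV-01-005.** Sections 16.2.2 and 16.4.2 of that sub-protocol SAP both defer to the Master SAP ("Details are provided in the Master COV-01 SAP"). Sections 16.2.3.1 and 16.4.3 report Day 29 and Day 60 mortality by arm with exact intervals, and both belong to the one final analysis.

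**The concern.** Both endpoints are cumulative from the start of the study, so the Day 60 window contains the Day 29 window. A patient counted as dead in the first has to be dead in the second. The two rules do not respect this: the Day 29 hospice imputation is confined to the main analysis of that endpoint, and nothing in Section 16.4 carries it forward.

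What is at stake is how the two tables read together. A reader will subtract Day 29 from Day 60 to see late deaths, and part of that difference can come from the change of rule. If the affected patients are unevenly spread, the difference between arms also shifts between horizons for the same reason, and could be mistaken for a late treatment effect.

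**Working it through.** **Plan figures used as context.** The Master SAP (Section 7.1) assumes 15% control mortality through Day 29, 8.25% on the agent, 350 per arm and 80% power. With unpooled variance the standard error is √(0.15×0.85/350 + 0.0825×0.9175/350) = 0.0241, and Φ(0.0675/0.0241 − 1.96) = 80.0%; pooled variance gives 79.7%. The plan's figure reproduces and is not in dispute. It supplies only the arm size and a plausible death count.

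**One patient under both rules.** Take a patient scored 7, discharged to hospice, who leaves the study on Day 20 with no Death Details record and no later contact.

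| Step | Through Day 29 | Through Day 60 |
|---|---|---|
| Recorded death? | No | No |
| Vital status | Unknown | Unknown |
| Hospice exception? | Yes (16.2.2.1) | None (16.4.2) |
| Counted as | Dead | Alive |

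This needs no assumed number.

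**Arm level.** Let n be the arm size, d the recorded deaths through Day 29, h the hospice patients imputed as dead at Day 29 whose status stays unknown, and x the recorded deaths from Day 30 to Day 60.

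- Day 29 mortality = (d + h)/n
- Day 60 mortality = (d + x)/n
- Day 60 falls below Day 29 exactly when h > x.
- Each affected patient is worth 1/350 = 0.29 points.

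Illustration with n = 350 and d = 52 (about 15%). The values of h and x are assumptions, because the documents give neither:

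| h | x | Day 29 | Day 60 |
|---|---|---|---|
| 0 | 2 | 54 − 2 = 52/350 = 14.86% | 54/350 = 15.43% |
| 1 | 2 | 53/350 = 15.14% | 54/350 = 15.43% |
| 3 | 2 | 55/350 = 15.71% | 54/350 = 15.43% |
| 5 | 2 | 57/350 = 16.29% | 54/350 = 15.43% |
| 10 | 5 | 62/350 = 17.71% | 57/350 = 16.29% |

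With h = 0 nothing goes wrong. With h = 1 and x = 2 the totals still rise, but one patient is classified both ways. With h above x the table shows mortality falling over time.

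**Between arms.** With equal arms, the Day 29 risk difference contains the term (h on agent − h on placebo)/n and the Day 60 difference does not. An imbalance of one such patient moves the difference by 0.29 points between horizons.

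**COV-01-005.** Section 16 of its SAP says 108 patients were randomized into the sub-protocol across both of its arms. The active arm is therefore smaller than 108, and one affected active patient is worth more than 1/108 = 0.93 points.

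**The case against.** The case for leaving this alone has real substance.

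- **The group is narrow.** Four conditions must hold together: unknown status, last score 7, hospice discharge, and discontinuation before Day 29. Hospice discharge does not end follow-up, since the Day 15, 29 and 60 contacts continue after discharge by telemedicine. Protocol Section 7.3 also requires efforts to establish vital status, including from public sources. A hospice patient with a recorded death, or known to be alive, is unaffected. This stands.
- **The endpoint is minor.** Day 60 mortality is outside the testing hierarchy of Master SAP Section 7.4 and carries no inference. The tested Day 29 analysis keeps its own rule, with multiple imputation and a tipping-point analysis behind it (Section 16.2.4). This stands.
- **A coherent comparison is already planned.** The Kaplan-Meier summaries in Sections 16.2.5 and 16.4.5 censor patients who leave at their discontinuation date and impute no deaths, so their cumulative incidence cannot fall. This stands, although they do not repair the binary percentages, relative risk or odds ratio.

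Stronger readings are tempting and are not supported. A reader might infer that Day 60 mortality is understated by some known number of points. That would need a frequency the documents do not give, and would treat every such patient as having truly died, when their status is unknown by definition. A reader might also apply the roughly 7:1 imbalance in COV-01-005 SAP Section 4.5.2 to the 108 randomized patients to get an active-arm size. That ratio compares the active arm with the shared control under the Master definition, so it does not split the 108. Nor does COV-01-005 plan a relative risk or odds ratio for Day 60; its exposure is in the within-arm percentages.

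Finally, patients who go to hospice and leave between Day 29 and Day 60 create no contradiction, because the Day 29 exception does not cover them.

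**Conclusion.** The point holds as a logical inconsistency between two stated rules. A patient meeting the four conditions is dead through Day 29 and alive through Day 60, and nothing elsewhere in the Master SAP or the COV-01-005 SAP reconciles this. That conclusion rests on the text alone.

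The size is 0.29 points per affected patient at 350 per arm, and the visible reversal requires h > x. Since h is not given and may be small or zero, no overall bias can be stated. The effect is limited to the binary Day 60 summaries and their comparison with Day 29. No confirmatory conclusion depends on it. It is worth correcting because an impossible pattern in a mortality table is hard to explain afterwards and easy to prevent.

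**What to change.** Add to Master SAP Section 16.4.2: any patient counted as dead through Day 29, including through the hospice rule of Section 16.2.2.1, is counted as dead through Day 60; all other patients of unknown status are handled as now. COV-01-005 inherits this through its existing cross-reference.

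Optionally, apply the hospice rule also to patients discharged to hospice who leave before Day 60 with unknown status. This is not needed to remove the contradiction. It would match how the Master SAP treats hospice discharge elsewhere: pooled with death in the ordinal distribution (16.2.1.4), scored as death for the worst score (16.2.1.5), given the worst value for ICU days (16.2.1.6), and imputed as death when a later score is missing (16.2.2.2).

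The cost is one sentence and reuse of the Day 29 hospice flag. No new data are needed and no tested analysis changes.
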